1.0 INTRODUCTION

1.1 Study Purpose

To determine the Clinical Accuracy of the welloStationX by:

- evaluating clinical bias with stated uncertainty; and
- determining clinical repeatability.

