4.2 Primary Outcome Analysis

As per ISO 80601-2-56, these measures will be recorded and analyzed as follows:

1. *Clinical Accuracy* will be evaluated by comparing the first recorded measurement using the welloStationX with the single measurement recorded by the Welch Allyn SureTemp oral thermometer.

Results will be presented through:

- (i) Descriptive presentation of means and standard deviations
- (ii) Evaluation of agreement calculated as the clinical bias (mean bias (\pm SD))
- (iii) Limits of Agreement (LOA) calculations
- (iv) Band-Altman plot created using mean bias and standard deviation data
- (v) XY Plot and Correlation Coefficient calculation

2. Repeatability will be calculated using the pooled standard deviations formula.

All analyses will be performed and presented by febrile status (febrile and afebrile) and by device (test device compared with reference device), as applicable.

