4.3 Study Success Evaluation

Accuracy and reliability in welloStationX thermometer readings will be demonstrated if there is close agreement between the welloStationX and the reference device (Welch Allyn SureTemp oral thermometer).

Additionally, agreement values will be referenced against those attained for the prior validation study for the CareGiver thermometer, with agreement values for the welloStationX to be comparable or better to the published data for the Caregiver. This reference is the following:

**Clinical validation of the CAREGIVER[®] non-contact thermometer model
PRO-TF200/PRO-TF300 in febrile and afebrile patients of all ages**

Naja E. [name], Alice Huang & Gary O'Hara MSE

November 2013 Copyright ©2013 Thermomedics[®], Inc.

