Wello Inc.

**CLINICAL RESULTS REPORT FOR THE STUDY:
WELLOSTATIONX DETERMINATION OF
CLINICAL ACCURACY; SEPTEMBER 21, 2018.**

NCT#: NCT03758157

November 28, 2018

Table of Contents

OVERVIEW

1.	Study Background and Purpose	3
2.	Study Device: welloStationX®	3
3.	Study Design	3
4.	Subject Sample	4
5.	Study Procedures	4

RESULTS

6.	Sample Demographics	5
6.1	Gender.....	5
6.2	Age.....	5
6.3	Ethnicity.....	6
7.	Clinical Accuracy	7
7.1	Mean and Standard Deviations	7
7.2	Clinical Bias.....	7
7.3	Limits of Agreement and Bland Althman Plots	7
7.4	XY Plot and Correlation Coefficient.....	8
8.	Clinical Repeatability	9
9.	Safety Evaluation	9
	DISCUSSION	10
	CONCLUSION	11

OVERVIEW

1. Study Background and Purpose

Following initial review of K180298 submitted by Wello, Inc (the Sponsor) for the welloStationX® (the device), the Sponsor received a Deficiency Letter from the FDA on August 2018 requesting provision of appropriate clinical accuracy testing as per standard regulations. Subsequently, Wello, Inc. conducted the requested clinical study to demonstrate clinical accuracy validation of the welloStationX® based on *ISO 80601-2-56 Medical electrical equipment — Part 2-56: Particular requirements for basic safety and essential performance of clinical thermometers for body temperature measurement*.

The primary objective of the study was to determine the Clinical Accuracy of the welloStationX® by:

- evaluating clinical bias with stated uncertainty; and
- determining clinical repeatability.

The results of this clinical study are intended to support the following indications for use: “The welloStationX is a non-contact device intended for use to measure the body temperature of individuals five years of age and older. The welloStationX can be used by medical professionals or laypersons in any public or private indoor facility including home use. The welloStationX has an ambient operating temperature range of 59F – 82.4F (15C – 28C).”

The study lasted approximately four weeks during September and October 2018.

2. Study Device: welloStationX®

The welloStationX® is an automated No-Touch Self-Service Electronic Thermometer designed to provide an accurate temperature reading without the time and exposure of a skilled attendant to the possibility of infection.

The welloStationX® is an electronic thermometer using an infrared sensor of the surface of the forehead adjusting human body skin temperature to oral thermometer without contact.

3. Study Design

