7.2 Clinical Bias

Agreement through clinical bias evaluation was calculated as the Mean Bias \pm SD by subtracting the first output measurement recorded with the welloStationX thermometer (DUT) from the corresponding output measurement recorded with the Welch Allyn SureTemp oral thermometer for each subject, and then calculating the Mean Bias \pm SD of the biases.

Table 5 below shows clinical bias by febrile status.

Table 5: Clinical bias by febrile status.

Mean bias \pm SD Febrile (n=33)	Mean bias \pm SD Afebrile (n=77)	Mean bias \pm SD All (n=110)
0.25 °F \pm 0.33	-0.06 °F \pm 0.42	0.03 °F \pm 0.42

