7.4 XY Plot and Correlation Coefficient

To further demonstrate the closeness of the relationship between the welloStationX (DUT) and the SureTemp (reference) readings, an XY plot of the two sets of readings was created and is shown in Figure 3 below.

[figure not shown]

Figure 3: XY Plot of welloStationX versus SureTemp for all subjects

$R^2 = 0.80$, indicating a strong linear relationship

8. Clinical Repeatability

Clinical Repeatability was calculated using the pooled standard deviations of the triplicate measurements recorded by the welloStationX.

Table 5 below shows clinical repeatability by febrile status.

Table 5: Clinical repeatability of the welloStationX by febrile status.

Febrile (n=33)	Afebrile (n=77)	All (n=110)
0.13	0.09	0.06

9. Safety Evaluation

There were no observed or reported adverse events for any subject in the study.

DISCUSSION

The results of this clinical study are interpreted both with respect to the study dataset alone and compared to the research data published in the following whitepaper:

Clinical validation of the CAREGIVER® non-contact thermometer model PRO-TF200/PRO-TF300 in febrile and afebrile patients of all ages

Naja E. [name], Alice Huang & Gary O'Hara MSE

November 2013 Copyright ©2013 Thermomedics®, Inc.

This comparison was selected for the following reasons:

1. The reported study clinical data was that which was submitted to the FDA in support of market clearance for the Caregiver Professional Clinical Thermometer (K131771) which is the predicate device in the current submission for K180298.
2. In the reported study, the reference thermometer used was the Welch Allyn SureTemp oral thermometer, the same reference thermometer used in the welloStationX clinical precision study.

There were no notable differences in gender, age or ethnicity by febrile status and age distributions across the spectrum was well represented. Therefore, the subject population was across febrile status was homogenous and the sample overall representative of the intended patient population.

The limits of agreement for the welloStationX are (+0.86, -0.80) which is better than that for the Caregiver study whose limits of agreement was (+0.82, -1.21).

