From the Bland Altman Plot, it is found that only four data points lie just outside the limits of agreement (such that 96.4% of all data points lie within the limits of agreement) which indicates there is a strong agreement between the performance of the welloStationX and the SureTemp and is fewer than the six outliers found in the Caregiver study, most of which also lay further away from the limits of agreement than the four outliers in the welloStationX study.

The limits of agreement did not exceed 0.86 (absolute value) and clinical bias did not exceed 0.03°F for the study population overall. These strong indicators of the close agreement between the performance of the welloStationX and the SureTemp are also superior to those attained in the Caregiver study, where the limits of agreement did not exceed 1.21 (absolute value) and clinical bias did not exceed 0.20 °F for subjects overall.

The highest bias attained was 0.25°F for subjects in the welloStationX febrile subject group, which is still notably lower than the greatest bias attained in the Caregiver study of 0.32°F for subjects in the afebrile group.

The XY Chart further demonstrates the close agreement between the performance of the welloStationX and the SureTemp. The correlation coefficient of 0.80 supports this strong linear relationship.

The notably low clinical repeatability of 0.062 for subjects overall indicates that the absolute difference in repeat measurements taken with the welloStationX is very low and therefore precision across repeated temperature readings is very strong and highly repeatable. Clinical repeatability was comparably high for both the febrile and afebrile subject groups in the welloStationX study, at 0.13 and 0.09, respectively. Each of these clinical repeatability values for the welloStationX thermometer is notably lower than those attained for the Caregiver (0.17 for subjects overall; 0.21 for the febrile subject group and 0.15 for the afebrile subject group).

CONCLUSION

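### No confidence interval is planned or reported for bias or limits of agreement, and two of the report's arguments against the Caregiver do not survive one

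*Protocol*

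**What the plan says.** Protocol 1.1 gives the first aim as "evaluating clinical bias with stated uncertainty". Protocol 4.2 then lists means and SDs, mean bias ± SD, limits of agreement, a Bland-Altman plot and a correlation, and adds: "All analyses will be performed and presented by febrile status (febrile and afebrile) and by device (test device compared with reference device), as applicable". No confidence interval appears in that list. Protocol 4.3 asks for close agreement with the oral thermometer and, in addition, a comparison with the Caregiver study, "with agreement values for the welloStationX to be comparable or better to the published data for the Caregiver", without a margin or an interval.

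The document supplied as the SAP is a results report dated November 2018: "The study lasted approximately four weeks during September and October 2018". Section 7.2 tabulates bias ± SD by febrile status. Section 7.3 gives one pooled pair of limits, +0.86 and -0.80°F. The Discussion makes three comparative statements:

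- On the limits: "The limits of agreement for the welloStationX are (+0.86, -0.80) which is better than that for the Caregiver study". The Caregiver's are given as +0.82 and -1.21.
- On the largest group bias, 0.25°F in febrile subjects: "which is still notably lower than the greatest bias attained in the Caregiver study of 0.32°F for subjects in the afebrile group".
- On the plot: "such that 96.4% of all data points lie within the limits of agreement", with four outliers set against six in the Caregiver study.

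**The concern.** An SD describes how differences spread between subjects. It does not say how precisely the mean bias, or a limit of agreement, has been estimated. In the febrile group the SD is 0.33 but the standard error of the mean bias is 0.057. A comparison of mean biases with another study needs the second quantity, and Protocol 4.3 makes such a comparison part of success.

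Without intervals, the report can present a 0.07°F gap as a notable advantage, and the reader cannot tell which predicate comparisons the data carry. The device is being evaluated for fever screening (Protocol 2.0 and 3.1), so how well febrile bias is known matters. At stake is what the report may claim, not whether the study is valid.

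**Working it through.** **Inputs.** Report Table 5: febrile 0.25 ± 0.33 (n=33), afebrile -0.06 ± 0.42 (n=77), all 0.03 ± 0.42 (n=110). Report 7.3: limits +0.86, -0.80. Discussion, for the Caregiver: limits +0.82, -1.21; overall bias 0.20; largest group bias 0.32 (afebrile). The Caregiver's N is not given. The documents state no confidence level; I assume two-sided 95%.

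**Reproducing the report's limits.** 0.03 ± 1.96×0.42 = +0.853, -0.793. The printed pair implies SD = (0.86+0.80)/3.92 = 0.4235, which rounds to 0.42. The figure reproduces within rounding.

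**Intervals for bias**, mean ± t×SD/√n:

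- Febrile: 0.25 ± 2.037×0.33/√33 = 0.13 to 0.37
- Afebrile: -0.06 ± 1.992×0.42/√77 = -0.16 to 0.04
- All: 0.03 ± 1.982×0.42/√110 = -0.05 to 0.11

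**Febrile bias against 0.32, taken as fixed.** t = (0.25-0.32)/(0.33/√33) = -1.22, df 32, p = 0.23. If the mean and SD each vary by ±0.005 for rounding, the upper bound runs from 0.360 to 0.374, so 0.32 is always inside. Sampling error in the Caregiver's value would weaken the claim further.

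**Intervals for the limits**, limit ± t×SD×√(1/n + 1.96²/(2(n-1))). Group limits are implied by Table 5; the report text does not print them.

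| Group | Upper limit (95% CI) | Lower limit (95% CI) |
|---|---|---|
| All (SD 0.4235) | +0.86 (0.72 to 1.00) | -0.80 (-0.94 to -0.66) |
| Febrile | +0.90 (0.70 to 1.10) | -0.40 (-0.60 to -0.20) |
| Afebrile | +0.76 (0.60 to 0.93) | -0.88 (-1.05 to -0.72) |

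**Direction of subtraction.** Section 7.2 describes "subtracting the first output measurement recorded with the welloStationX thermometer (DUT) from the corresponding output measurement" of the reference, that is, reference minus device. Table 4 gives 99.83 - 99.58 = +0.25 (febrile) and 98.15 - 98.22 = -0.07 (afebrile; Table 5 prints -0.06, a rounding difference). The printed signs are device minus reference.

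**Points inside the limits.** Limits of ±1.96 SD contain about 95% of roughly normal differences, whatever the SD. Expected outside: 0.05×110 = 5.5. Binomial P(4 or fewer) = 0.35.

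**What the other Caregiver comparisons depend on.** If the Caregiver's limits are ±1.96 SD, its SD is (0.82+1.21)/3.92 = 0.518.

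- Largest absolute limit: the gap is 1.21 - 0.86 = 0.35. Using the limit standard errors above, it exceeds 1.96 standard errors once the Caregiver's N is about 30.
- Width: ratio 1.66/2.03 = 0.818. The F-based 95% upper bound is 1.03 at N=50, 1.00 at N=75, and first falls below 1 at N=83.
- Overall bias: the Caregiver's midpoint is (0.82-1.21)/2 = -0.195. Taking the less favourable case of equal signs, the gap is 0.195 - 0.03 = 0.165. Then N = 0.518²/((0.165/1.96)² - 0.4235²/110), about 50.

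**Case mix.** The group biases differ by 0.31, with standard error √(0.33²/33 + 0.42²/77) = 0.075, z about 4.1. The overall 0.03 is therefore a weighted average at 30% febrile. At 50%, the top of the range in Protocol 3.2.1, it becomes 0.5×0.25 + 0.5×(-0.06) = 0.095. The gap falls to 0.10, and the same formula, keeping SD 0.4235, needs N of about 276.

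**Consistency of the febrile group.** If all 33 febrile subjects read at least 99.5°F orally with mean 99.58 (at most 99.585 before rounding), the largest possible SD puts all the excess in one subject: 0.085×√33 = 0.49. Table 4 prints 0.71.

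**The case against.** The report compares its worst group with the Caregiver's worst group and prints the afebrile label. It claims neither statistical significance nor better febrile accuracy. That stands: the fault is the strength of the wording on a 0.07°F gap, and the mismatch of groups, not a concealed febrile claim.

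The word *better* for the limits is also less bare than it looks, because the Discussion goes on to give the largest absolute limit as its yardstick. On that measure, and on width, the point estimates do favour the device. A reader might infer from +0.86 against +0.82 that the device is worse on one side. The documents do not support that. The 0.04 gap is well inside an uncertainty of about ±0.14, the report makes no side-by-side claim, and the Caregiver's sign convention is not given.

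The sponsor could say that SD and limits are the uncertainty its standard intends. Protocol 4.2 invokes ISO 80601-2-56, which is not available here, so a breach of that standard should not be inferred. It remains true that an SD cannot support a comparison of mean biases.

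Protocol 4.2 qualifies its request for results by febrile status with *as applicable*, and Figure 2 cannot be seen. Since group limits follow from Table 5, leaving them out is a minor reporting gap.

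A reader might also infer that the Caregiver was more accurate in febrile subjects. If its overall 0.20 were a weighted mean with afebrile bias 0.32 and 30 to 50% febrile, its febrile bias would be (0.20 - 0.7×0.32)/0.3 = -0.08 to (0.20 - 0.5×0.32)/0.5 = +0.08. That assumes signs and case mix the documents do not give, so it is a reason to consult the cited paper and not a finding.

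**Conclusion.** The point holds. No interval is planned or reported, and the report's own figures give a febrile bias of 0.25°F with 95% CI 0.13 to 0.37, which includes 0.32. The notably-lower claim and the coverage and outlier arguments should go. The subtraction described in section 7.2 is the reverse of what the tables show.

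The smaller largest limit and the narrower width stand as point estimates. Anything stronger depends on the Caregiver's N, and the overall bias comparison depends on febrile share in both studies as well.

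A reader might conclude that the success criterion was missed. It is not shown to have been: comparability has no margin, and no value is shown to fail it.

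The intervals assume roughly normal differences and Table 5 as printed; those for the pooled bias and limits also describe this study's case mix. The febrile interval carries a further caveat. The Table 4 oral SD of 0.71 cannot arise if fever was classified by the oral reading at 99.5°F, so either the classification (the report speaks of core temperature) or the table needs reconciling before that interval is relied on.

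**What to change.** Make the changes in the report and label them post hoc, since the study is complete and the results are known. Do not rewrite the Protocol 4.3 success rule as though intervals had been prespecified.

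- Reconcile the febrile classification with the Table 4 oral SD.
- Correct the description in section 7.2 to device minus reference.
- Add 95% CIs for mean bias and for both limits, overall and by febrile group, computed from subject-level data.
- Delete the notably-lower statement and the 96.4% and outlier-count arguments.
- Describe the limits as better only in the sense of a smaller largest absolute limit and a narrower width, as point estimates unless the Caregiver's N is brought in.
- Compare febrile with febrile and afebrile with afebrile where the cited paper gives the figures.
- State that the overall bias comparison depends on case mix and on the Caregiver's N.

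The cost is a short edit and calculations on existing data, with no new subjects. Whether the cited paper prints its group biases, N and sign convention cannot be confirmed from these documents. The downside for the sponsor is a less favourable comparison with the predicate and a visible post hoc label.

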The study was a non-randomized, non-blinded single arm design with the subject as his or her own control to evaluate the clinical accuracy of the welloStationX thermometer with respect to that of the standardized Welch Allyn SureTemp oral thermometer in the screening of individuals with fever.

4. Subject Sample

Subjects were 110 males and females aged 5 years of age and older: 33 subjects (30%) were febrile, with fever defined as a core temperature of 99.5°F (37.5°C) or higher; and 77 subjects were afebrile.

Subjects were recruited from amongst non-profit clinical sites and through social media posts for subjects to come to a test site or to be evaluated in his or her own home in the widespread Dallas/Fort Worth area.

Afebrile subjects were compensated with a \$10 gift card and febrile subjects were compensated \$25, the additional amount intended to assist the febrile subject to recovery.

5. Study Procedures

Each subject's temperature was measured three separate times sequentially using the study device, the WelloStationX® (*DUT*) and one time using a new off-the-shelf calibrated Welch Allyn SureTemp oral thermometer with disposable probe covers (the reference thermometer). Each measurement was recorded by a trained technician by following the instructions for use contained in the respective device labeling.

Subject age, gender and race were recorded for each subject, and potential adverse event observation was conducted.

A subject or the subject's guardian was immediately informed if a febrile temperature measurement (99.5°F (37.5°C) or higher) was recorded using the Welch Allyn SureTemp oral thermometer. The subject or guardian will be advised to consider seeking medical attention.

RESULTS

6. Sample Demographics

The sample demographics of gender, age and race are shown below in Tables 1 through 3, respectively, for febrile and afebrile subjects and for subjects overall.

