7.1 Means and Standard Deviations

Table 4 below shows the mean and standard deviation of temperature readings in °F with the welloStationX (DUT) and the Welch Allyn SureTemp (reference thermometer) by febrile versus afebrile subject groups.

Table 4: Means and Standard Deviations by Febrile Status

Temperature Reading (°F)	welloStationX Febrile (n=33)	Welch Allyn Febrile (n=33)	welloStationX Afebrile (n=77)	Welch Allyn Afebrile (n=77)
Mean	99.83	99.58	98.15	98.22
Standard deviation	0.60	0.71	0.47	0.29

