The intent of this study was to clinically validate application of the welloStationX automated no-contact thermometer to the reference device, the Welch Allyn SureTemp oral thermometer. The validation results indicate a high level of agreement between the welloStationX and the SureTemp. Repeatability across three sequential measurements with the welloStationX indicated high precision. It can be concluded that the welloStationX automated non-contact thermometer is an accurate and reliable tool to measure body temperature of individuals five years of age and older.

END OF DOCUMENT

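### On bias and the largest pooled limit of agreement, the Caregiver comparison would still be passed with the afebrile readings randomly re-paired, so passing it does not show individual-level agreement in afebrile subjects

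*Protocol*

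**What the plan says.** Protocol 4.3 has two success statements. Accuracy and reliability "will be demonstrated if there is close agreement between the welloStationX and the reference device"; in addition, it wants "agreement values for the welloStationX to be comparable or better to the published data for the Caregiver". Neither has a numeric margin, a confidence interval or a separate requirement for afebrile subjects. Protocol 4.2 asks for the analyses by febrile status, as applicable.

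The filed SAP document is a results report. In its sample, "33 subjects (30%) were febrile" and "77 subjects were afebrile". Section 7.3 gives limits of agreement only for all 110 subjects (+0.86, -0.80), and section 7.4 gives R² only for all subjects (0.80). The Discussion compares with the Caregiver study on five items:

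- limits of agreement: largest absolute value 0.86, whereas for the Caregiver "the limits of agreement did not exceed 1.21 (absolute value";
- overall bias: 0.03 against 0.20°F;
- highest group bias: 0.25 against 0.32°F;
- points outside the limits: four against six;
- repeatability: 0.06/0.13/0.09 against 0.17/0.21/0.15 (overall/febrile/afebrile).

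The Conclusion calls the device an "accurate and reliable tool to measure body temperature of individuals five years of age and older".

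**The concern.** A claim to measure an individual's temperature needs evidence that the device reading follows that individual's reference reading. Mean bias does not depend on which device reading is paired with which subject. Nor does repeatability, as long as each triplicate stays together. Of the items compared, only the limits of agreement, and the outlier count derived from them, respond to pairing. Afebrile readings vary little, so even unrelated pairs differ by only modest amounts. If the benchmark is wide enough to admit unrelated pairs, passing it says little about individual agreement in 70% of the sample, and the Conclusion rests there on a comparison that did not test it.

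**Working it through.** **Inputs.** From "Table 4: Means and Standard Deviations by Febrile Status", the row "Standard deviation 0.60 0.71 0.47 0.29" gives SDs in °F for febrile device, febrile oral, afebrile device and afebrile oral readings; the means in the same order are 99.83, 99.58, 98.15 and 98.22. The bias table in section 7.2 gives 0.25 ± 0.33 febrile (n=33), -0.06 ± 0.42 afebrile (n=77) and 0.03 ± 0.42 overall. The Discussion gives Caregiver limits of +0.82 and -1.21, a width of 2.03.

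**Reproducing the report's pooled figures.**
- Mean = (33×0.25 - 77×0.06)/110 = 0.033.
- SD = sqrt{[32×0.33² + 76×0.42² + (33×77/110)×0.31²]/109} = sqrt[(3.485 + 13.406 + 2.220)/109] = 0.419.
- Limits = 0.033 ± 1.96×0.419 = (+0.85, -0.79), against the reported (+0.86, -0.80).

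**Implied within-group correlation**, r = (SDx² + SDy² - SDd²)/(2·SDx·SDy).
- Febrile: (0.3600 + 0.5041 - 0.1089)/(2×0.60×0.71) = 0.89.
- Afebrile: (0.2209 + 0.0841 - 0.1764)/(2×0.47×0.29) = 0.47, so R² is about 0.22. Rounding of the inputs allows r from 0.44 to 0.50.

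**Check against the reported R².**
- Cross-products: febrile 32×0.3776 = 12.08; afebrile 76×0.0643 = 4.89; between groups 23.1×1.68×1.36 = 52.78; total 69.75.
- Sums of squares: 93.51 (device) and 65.25 (oral).
- R² = 69.75²/(93.51×65.25) = 0.80, as reported, so the tables are mutually consistent. About 76% of the cross-product (52.78/69.75) is the gap between the febrile and afebrile means, and 7% comes from within the afebrile group.

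**Random re-pairing of the 77 afebrile device readings** (expected afebrile covariance zero, all else unchanged).
- Afebrile SD of differences = sqrt(0.47² + 0.29²) = 0.55, against 0.42 observed.
- Pooled SD = sqrt[(3.485 + 76×0.305 + 2.220)/109] = 0.515.
- Limits = 0.033 ± 1.96×0.515 = (+1.04, -0.98); width 2.02.
- Pooled R² = (69.75 - 4.89)²/(93.51×65.25) = 0.69.

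**Each comparison after re-pairing.** Shuffle percentages come from 40,000 permutations of normal data matched to the reported moments.

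| Item | Re-paired | Caregiver | Result |
|---|---|---|---|
| Largest absolute limit | 1.04 (1.03 to 1.06 over rounding) | 1.21 | passed in every shuffle; maximum 1.19 |
| Overall bias | 0.03 | 0.20 | unchanged |
| Highest group bias | 0.25 | 0.32 | unchanged |
| Width of limits | 2.02 (1.99 to 2.05 over rounding) | 2.03 | about a tie; passed in about 56% |
| Points outside own limits | mean 5.6 | 6 | fewer than six in about 49% |
| Repeatability | unchanged if triplicates stay together | | unchanged |

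**What the largest-limit comparison does exclude.** The limit reaches 1.21 when the pooled SD is (1.21 - 0.033)/1.96 = 0.60. The afebrile SD of differences is then sqrt[(109×0.6005² - 3.485 - 2.220)/76] = 0.66.

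**Limits by group from the reported figures.** Febrile: 0.25 ± 1.96×0.33 = -0.40 to +0.90°F. Afebrile: -0.06 ± 1.96×0.42 = -0.88 to +0.76°F. Both groups have a limit beyond the 0.86 that the report gives as its maximum.

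**The case against.** **Not every comparison survives re-pairing.** This stands. By width the shuffled data only tie with the Caregiver, and the outlier count beats six in about half of shuffles. The point therefore covers bias and the largest absolute limit. The report does use that limit: it calls its limits better although its upper limit (+0.86) is already worse than the Caregiver's (+0.82). The outlier count is taken against the study's own limits, which widen as agreement worsens, so it says little about agreement.

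**The rule does test something.** This also stands. A reader might infer that passing is no evidence of accuracy at all. The documents do not support that: accuracy under Protocol 4.2 includes bias and spread, and the comparison would catch a large offset or an afebrile SD of differences above about 0.66.

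**A correlation of 0.47 is not in itself poor agreement.** Agreed; a narrow temperature range lowers correlation. Nor do the data show an absence of tracking: 0.42 is below 0.55, and in febrile subjects 0.33 is far below the re-paired sqrt(0.60² + 0.71²) = 0.93.

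**A reader might also infer that the device does worse than a constant reading in afebrile subjects**, because Table 4 as labelled gives an oral SD of 0.29 against 0.42 for the differences. That depends on doubtful column labels:
- If status was set by the oral reading, which is not stated outright, 33 values of at least 99.5 with mean 99.58 can have an SD of at most 0.08×sqrt(33) = 0.46 (0.49 allowing for rounding). Table 4 shows 0.71.
- Section 7.2 defines bias as oral minus device, which gives the reported signs only if the columns are swapped.

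With the columns swapped, the constant's SD is 0.47 and the device's 0.42 is smaller. The inference cannot be drawn until the labels are reconciled. The re-pairing result is unaffected, since sqrt(0.47² + 0.29²) is the same either way.

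**Conclusion.** The concern holds in this limited form. On bias and the largest absolute pooled limit, as the report applies them, the Caregiver comparison would be passed with the afebrile readings randomly re-paired (1.04 against 1.21, biases unchanged). Passing it is not evidence of individual-level agreement in afebrile subjects. The pooled R² does not fill the gap, since it would still be about 0.69. This does not mean that the device fails to track afebrile temperature; it means that the cited comparison does not test it.

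The expected re-paired limits rest only on the reported moments and the arithmetic above. The shuffle percentages also assume normal readings, because individual data are not given. The Caregiver figures are taken as the report quotes them.

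**What to change.** In Protocol 4.2 and 4.3 and in the report:

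- Give limits of agreement with confidence intervals, and the correlation, separately for febrile and afebrile subjects, and base the agreement evaluation on them. From the reported figures the limits are about -0.40 to +0.90°F and -0.88 to +0.76°F. With the large-sample standard error SD×sqrt[1/n + 1.96²/(2(n-1))], each limit carries a 95% interval of roughly ±0.19°F (febrile) or ±0.16°F (afebrile).
- If useful, show the re-paired SD (0.55) beside the observed afebrile SD (0.42), as context and not as a pass/fail rule.
- Stop citing the pooled Caregiver comparison and pooled R² as individual-level evidence in afebrile subjects. Word the Conclusion to the group-specific limits, and drop the statement that the limits stay within 0.86 where it is read as applying to each group.
- Reconcile the Table 4 column labels with the bias definition in section 7.2 and with the fever cut-off before making any comparison against a constant reading.
- Record that the changed evaluation was made after the results were known.

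This is re-analysis of data already held plus changes of wording, with no new subjects or procedures. The price is a less favourable stated conclusion for afebrile subjects.
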